5.4 Methods of minimising bias

To account for the other influences on the prescribing practices of physicians, a controlled design has been chosen. Thus, external influence from medical literature, expert opinions, treatment guidelines or other sources should equally impact NHs in the intervention and control groups.

Randomisation will increase the likelihood that the characteristics of participating NHs are similar between the two groups. To account for the fact that some physicians are responsible for more than one NH, thus allowing for "bleeding" of the intervention between the two groups, randomisation will be clustered at the physician level (see section 5.3, page 13 for details).

Previous discussions with the prospective participants and their professional associations show that there is a great interest for deprescribing among partners. We fear that a purely controlled design will prevent the participation of some of the most interested NHs, thus minimising the effect of the intervention. To reduce this risk, we will offer the possibility to participants randomized to the control group to enact the intervention one year after the start of the study. At this point, all NH in the intervention group will have submitted to the intervention and its effects will have full deployed.

Finally, assessments of the study outcomes will be conducted while maintaining allocation blinding, ensuring that no analysis bias occurs.

Given that the unit of analysis is the NH, the risk of loss to follow-up is deemed inexistent. Data collection will take place in the same way as it already routinely does in a satisfactory way, thus reducing the risk of missing data.

6. PROJECT POPULATION

6.1 Inclusion criteria

This study is open to all NH of Vaud and Fribourg:

- Who have been part of their cantonal pharmaceutical assistance programme for more than 1 year at the time of recruitment;
- Who have a geriatric or psychogeriatric mission, or a mainly geriatric population;
- Whose residents' mean age is at least 65 years.

6.2 Exclusion criteria

No exclusion criteria will be enforced.

6.3 Criteria for withdrawal / discontinuation of participants

Participating NHs will have to withdraw from the study if one of the partners (physician, head nurse, pharmacist or NH direction) withdraws its consent to participate, if the mission of the NH become exclusively psychiatric, or if the mean age of its residents becomes less than 65 years.

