8.3.1 Datasets to be analysed

All retrospective data collected will be used for the main analysis. If some NH allocated to the intervention group do not hold the QC session but provide their data, they will be included in the analysis. The statistician performing the analysis will be blinded to the allocation; groups will be identified as A and B.

Subgroups analysis will be made, both for the primary and secondary outcomes, for the following subgroups:

- NH of Vaud;
- NH of Fribourg;
- NH with a geriatric mission;
- NH with a psychogeriatric mission;
- NH having held the QC session.

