## Inferential analysis

The analysis will follow the intention to treat approach. However, it is expected that all NH comply with the intervention group they have been randomized into.

No formal statistical tests will be applied to compare NH groups for the variables measured before randomization.

If the primary outcome follows a normal distribution and variances between intervention groups are equal, NH groups will be compared by means of linear least-square regression under adjustment for baseline. In case of heteroscedasticity, a robust estimation of the variance will be applied. If the outcome does not follow a sufficiently normal distribution, a generalised linear model (GLM) will be applied with the most appropriate distribution and link function. Residual diagnostics will be used to check the quality of the statistical model. If it is not possible to find an acceptable model, the two NH groups will be compared by means of a Mann-Whitney test without baseline adjustment.

The same procedure will be used to compare the differences between baseline and 12 months for the proportion of probably inappropriate galenic units and of possibly inappropriate galenic units (two variables), the proportion of probably inappropriate DDDs and of possibly inappropriate DDDs (two variables) and for mortality rate.

The number of hospital days/mean resident/year, number of falls/mean resident/month; and number of restraint measures/mean resident/month, being counts, are likely to follow a Poisson distribution. Therefore, a GLM with family Poisson and logarithmic link function will be applied first.

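### The compulsory withdrawal rule in section 6.3 conflicts with the claim of no loss to follow-up and, combined with the complete-case rule in 8.3.2, undermines the intention-to-treat analysis

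*Protocol*

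**What the plan says.** - **Protocol 6.3** makes exit compulsory on partner withdrawal: "Participating NHs will have to withdraw from the study if one of the partners" (physician, head nurse, pharmacist or NH management) takes back consent. Two further triggers concern the NH itself: "if the mission of the NH become exclusively psychiatric, or if the mean age of its residents becomes less than 65 years".
- **Protocol 5.4**: "Given that the unit of analysis is the NH, the risk of loss to follow-up is deemed inexistent".
- **Protocol 8.3.1**: "All retrospective data collected will be used for the main analysis". It adds: "If some NH allocated to the intervention group do not hold the QC session but provide their data, they will be included in the analysis".
- **Protocol 8.3.2** expects no missing data, yet allows for drop-out. It excludes an NH without drug consumption data from all analyses, and an NH lacking a secondary outcome from that analysis only.
- **SAP, Inferential analysis**: "The analysis will follow the intention to treat approach". The SAP does not define the term further. Its only provision on missing values is to check for them and count them.
- **Protocol 5.3 and 7.2**: the drug data behind the primary outcome come from the routine monitoring of the cantonal programmes and are anonymised before the investigators receive them. Falls and restraint use are instead entered by nurses in the NHs.

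**The concern.** Each trigger in 6.3 is something that happens after randomisation. Section 5.4 rests its claim on the NH being the unit of analysis, but 6.3 provides for the loss of exactly that unit.

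A comparison by randomised group is protected only if post-randomisation events do not decide who is analysed. Reasons for a partner to step back may be related both to arm and to outcome. The course, the session, the consensus, the annual-report chapter and most questionnaires fall on the intervention arm. A partner who dislikes deprescribing may also work in an NH where prescribing changes little. If such NHs disappear from the analysis, the contrast is no longer between the groups as allocated.

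Losses may also come in groups. Section 5.3 says that some physicians serve several NHs, and NHs sharing a physician are allocated together. One physician's withdrawal can therefore remove more than one NH from the same arm.

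**Working it through.** **Step 1. Follow three NHs through the rules.**

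| NH | 6.3 | Analysis rule that applies |
|---|---|---|
| A: intervention arm, never holds the session, all partners stay | Stays | 8.3.1: analysed if it provides data |
| B: intervention arm, never holds the session, one partner withdraws consent | Must leave | None stated. If no follow-up drug data are passed on, 8.3.2 excludes it from all analyses |
| C: either arm, mean age falls below 65 or mission becomes exclusively psychiatric | Must leave | As for B |

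A and B have the same exposure to the intervention. They differ only in whether a partner formally withdrew. For C, 5.3 collects mission and mean age every year, so the trigger would be read from follow-up values.

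**Step 2. Is zero loss plausible under 6.3?** The documents give no withdrawal rate, so this is an assumption: each of four partners withdraws independently with probability q. The chance that an NH must leave is 1 − (1 − q)^4.

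- q = 1%: 1 − 0.99^4 = 3.9%. Of the synopsis's 62 NHs, 62 × 0.0394 = 2.4 leave, and the chance of losing at least one is 1 − 0.99^248 = 92%.
- q = 2%: 1 − 0.98^4 = 7.8%, or 4.8 of 62.

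**Step 3. Does the sample size absorb losses?** First, the plan's own figure. Section 8.1 has a 4.6-point difference, SD 7.5, 80% power and 66 NHs. With n per group = 2(z_α + z_β)² SD²/δ²:

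- one-sided 5%: 2 × (1.645 + 0.842)² × 7.5²/4.6² = 32.9, so 33 per group and 66 in all, which reproduces the plan;
- two-sided 5%, the level in 8.3: 2 × (1.960 + 0.842)² × 7.5²/4.6² = 41.7, so 42 per group and 84 in all.

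On either basis there is no allowance for loss. Section 8.3.2 refers to a supplementary recruitment in 8.1 that 8.1 does not contain. The second round in 5.2 is triggered by insufficient recruitment. (The 62 versus 66 and the sidedness discrepancies are separate points.)

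Starting from 66, with assumed losses spread evenly over the arms:

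| Loss | Power, one-sided | Power, two-sided | Randomise to keep 66 |
|---|---|---|---|
| 0% | 80.1% | 70.2% | 66 |
| 5% | 78.3% | 68.0% | 70 |
| 10% | 76.4% | 65.7% | 74 |
| 20% | 72.0% | 60.6% | 83 |

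**Step 4. How large could a bias be?** If a fraction p of one arm is removed, and the removed NHs differ from the retained ones by d points in mean change, that arm's mean shifts by p × d. Both inputs are assumptions.

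- p = 10%: 0.10 × 3 = 0.30 to 0.10 × 4.6 = 0.46 points, or 7% to 10% of the 4.6-point target.
- p = 5% with d = 3: 0.15 points (3%). p = 20% with d = 4.6: 0.92 points (20%).

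For scale, the standard error of the unadjusted difference with 31 per group is 7.5 × √(2/31) = 1.9 points. The 10% case is 0.30/1.905 = 0.16 to 0.46/1.905 = 0.24 standard errors. The sign depends on which arm loses NHs and whether those NHs did better or worse. Equal, similar losses in both arms cancel.

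**The case against.** The strongest reply is that 6.3 speaks of leaving the study, not of leaving the analysis. With 8.3.1 using everything collected, routine monitoring as the source of the drug data, and the SAP stating intention to treat, the sections can be read together: participation stops and the data are still analysed. This stands in part. A reader might infer that 6.3 contradicts intention to treat outright, but the text does not go that far. The sections do not enforce the benign reading either. The provision in 8.3.1 for non-adherent NHs depends on their providing data and does not mention withdrawn ones, and the ordinary sense of withdrawing from a study is that no further data are used.

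A reader might also infer that removals would flatter the intervention because only that arm carries extra work. The documents do not support this. Section 5.3 has nurses reporting NH-level data without restriction to one arm, and 5.1 confines most, not all, of the implementation evaluations to the intervention group. Section 5.4 worries about keen NHs being put off by a control condition and offers them the module later. Section 11 describes remuneration in Vaud and a grant request for Fribourg. The workload argument also says nothing about the mission and age triggers, which are narrow and have no evident link to arm.

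Finally, the agreement to participate (Annex 2) is not in the text available for this review. It may already say what happens to data on withdrawal, so no claim is made that it is silent.

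**Conclusion.** The conflict between 6.3 and 5.4 is plain: one section sets out compulsory exits for randomised NHs and the other says that none can be lost, while 8.3.2 itself provides for drop-out. The weakening of intention to treat is conditional. It follows if withdrawal ends the use of data, because 8.3.2 then removes the NH from all analyses. In that case, NHs with the same exposure are treated differently and two follow-up characteristics become grounds for exclusion.

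The size and direction of any bias cannot be established. The range of 0.15 to 0.92 points rests wholly on assumed removal rates and differences, and could go either way. The power figures likewise rest on assumed losses. The point does not depend on these numbers. It rests on a stated rule that lets post-randomisation events decide who is analysed, where most of the needed data would exist regardless.

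**What to change.** 1. Reword 6.3 so that a partner's withdrawal ends study activities in that NH only. Its routinely collected monitoring data (drug consumption, days in the NH, hospital days, deaths) stay in the intention-to-treat analysis under the allocated group, unless a partner objects to their use. Any of the four partners should be able to object, since 5.2 requires the approval of all four.
2. State that a mission becoming exclusively psychiatric, or a mean age below 65, after randomisation does not remove the NH from the analysis.
3. Delete the statement in 5.4 that loss to follow-up cannot occur.
4. Align 5.4, 6.3, 8.3.1, 8.3.2 and the SAP's Inferential analysis section, and define the intention-to-treat set in the SAP.
5. Report withdrawals, with reasons, by arm.

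The cost is mainly wording. The agreement to participate may need a line on keeping aggregated routine data. The SAP describes allocation in the past tense, so agreements may already be signed and partners may have to be approached again.

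The change cannot secure everything. Falls and restraint use are reported by the NH and may still be missing after withdrawal. Hospital days and deaths are listed as monitoring data in 5.3 but described as NH-reported in 8.2 and the SAP, so their source should be settled at the same time.

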7. PROJECT ASSESSMENTS

7.1 Project flow chart

See Schedule of assessments, page 8.

7.2 Assessments of primary outcome

The primary endpoint of this study will be the difference in the overall proportion of PIMs used in each NH between baseline and 12 months. This endpoint will be assessed using the drug consumption data collected by the CPC monitoring team for the monitoring of the two cantonal PAPs; these data will be anonymised before transmission to the investigators (see section 5.3, page 13 for data collection).

PIM status for each line of drug consumption data will be assessed using a custom screening tool combining criterion from the Beers' list [6], STOPP tool [31] and NORGEP-NH list [32]. This tool will classify each data line as "not inappropriate", "possibly inappropriate" or "probably inappropriate". At both time points, the proportion of PIM will be computed for each NH as the ratio of the number of galenic units classified as "inappropriate" (sum of possibly and surely inappropriate) to the total number of galenic units used in the NH over the course of the past year. The primary outcome will be the difference of the two resulting proportions.

The co-primary endpoint for this study will be the change in the number of potentially inappropriate DDD/res between baseline and 12 months. For each NH, the total number of DDD used will be computed according to the active ingredient of the drug and its administration route. The total number of DDD will be divided by the total number of days spent in the NH for the year to calculate the number of DDD/res.

Rationale for the addition of a co-primary outcome: work on the same topic carried out by the investigators during the study revealed that the change in number of potentially inappropriate DDD/res is a more robust outcome, as it captures the adaptations of the doses of PIMs used and, unlike the proportion of potentially inappropriate galenic, is independent of the total amount of drugs. This addition of a co-

primary outcome was decided before the completion of data collection, and before any analysis of the data collected to date had been carried out. The investigators stress that this addition is in no way related to a supposed lack of effectiveness of the intervention; rather, it has been decided to try and reflect the effects of the intervention in the most accurate way possible.

7.4 Assessment of implementations outcomes

As the implement study is descriptive, all implementation outcomes (list available in Annex 1) will be summative.

8. STATISTICAL METHODOLOGY

8.1 Determination of sample size

Based on the retrospective data collected for the administrative monitoring of the Fribourg PAP, the mean proportion of PIM in the NH of Fribourg in 2015 was 22.8% (SD 6.3%). The natural year-on-year variation of the outcome was calculated between 2014 and 2015: the mean difference is 0.8% (IC₉₅ -1.1% - 2.7%, SD 5.3%); the correlation coefficient ρ between values of the outcome for 2014 and 2015 is 0.54 (IC₉₅ 0.29 – 0.72).

Studies of deprescribing have shown relative reductions in the number of PIMs ranging from 6.4% [33] to 31%[34]; one of the largest studies so far showed a 19.7% reduction in the number of PIMs [30]. Our hypothesis is that the intervention proposed in this study will reduce the proportion of PIMs used by 20%, in relative term.

We aim to detect an absolute difference of 4.6% ($22.8\% \times 0.2$) in the one-year reduction of the proportion of PIM between the control and intervention groups. The standard deviation of the difference at 12 months (SD_{diff}) was estimated with the following formula, assuming that the standard deviation at baseline and 12 months were the same and equal to 6.3%:

$$Var_{diff} = Var_{baseline} + Var_{12\;months} - 2 \cdot \rho \cdot SD_{baseline} \cdot SD_{12\;months}$$

By varying the correlation coefficient ρ along the confidence interval, plausible values of SD_{diff} were estimated to be between 4.1% (ρ =0.7) and 7.5% (ρ =0.3). A value of ρ =0.3 (SD_{diff} = 7.5%) was chosenas a conservative estimate for the calculation of the sample size, given the moderate correlation between the values for 2014 and 2015. To detect a difference between a mean difference of 0 in the control group and 4.6 in the intervention group (common SD of 7.5%, risks of α and β errors of 5% and 20%), 66NH, 33 per group, will have to be included. With an optimistic estimate of ρ = 0.7, the number of NH to include would decrease to 36. However, as this could lead to a lack of statistical power, a conservative estimate has been preferred.

Given that 82 NH meet inclusion criteria in the canton of Vaud and 42 in the canton of Fribourg, we expect that approximately 2/3 of the participants will be recruited in Vaud, and 1/3 in Fribourg.

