Project assessments, procedures:	Participating NHs will be randomised in two groups. NHs allocated to the intervention group will hold a QC session on deprescribing, where a local consensus on the deprescribing of specific therapeutic classes will be elaborated.									
	The effects will be assessed using anonymous data on the drug consumption of the NH (already routinely collected for the administrative monitoring of the pharmaceutical assistance programme) and NH-level data on falls, hospitalisation, emergency events and death. The implementation outcomes will be evaluated with questionnaires to health care professionals of the intervention group at baseline, 3 months and 12 months.									
Number of Participants:	62 NHs will be included in this project, 31 in each group (intervention and control). Assuming a normal distribution of the reduction in PIMs proportion and a standard deviation of 7.5%, similar between the two groups, this number of participant will allow for the detection of a 20% relative reduction in the primary outcome, from 22.8% to 18.2%, with 80% power.									
Project Duration:	From December 2017 to March 2019 (possible extension to March 2020)									
Project Centre(s):	Single-centre; the intervention will take place in multiple NHs in the cantons of Vaud and Fribourg.									
Statistical Considerations:	The inclusion of 62 NH will allow for the detection of a 20% relative reduction in the use of PIMs with 80% power.									
	The main outcome will be assessed using a generalised linear regression model taking the difference at 12 months in overall PIM proportion as dependent variable. The secondary outcomes will be assessed using the same methodology. The 5% level of significance will be considered for all analyses.									
Other methodological Considerations:	No other methodological considerations.									
Risk-Benefit statement:	In previous studies of deprescribing in older people residing in nursing homes, very few adverse events occurred, none of them serious. Moreover, physicians will retain complete control over NH residents' treatments during the study. It is thus estimated that the intervention poses little to no risk compared to usual care. Possible benefits include a reduced mortality rate and fewer adverse drug reactions, as well as fewer hospital stays and reduced consumption of acute care. The risk-benefits balance of this project is estimated to be clearly positive.									

ABBREVIATIONS

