8.3 Planned analysis

Descriptive statistics

Participating NH will be described, by group, in terms of number of beds, mean age of residents, mission (geriatric, psycho-geriatric or mixed), and number of nurses, physicians and pharmacists. Each implementation outcome (list available in Annex 1) will be presented with a suited summative data.

Inferential statistics

The main outcome is the difference in the overall proportion of PIMs used in the NH 12 months after intervention, relative to baseline. The primary analysis will test the difference in the overall proportion of PIMs between the intervention and control groups using a generalised linear regression model, taking the difference in overall proportion of PIMs at 12 months as the dependant variable, and the group allocation (binary variable) and baseline overall proportion of PIMs as independent variables (two-sided α = 0.05). The analysis will be made immediately after the completion of follow-up data collection.

The same analysis will be carried out for the co-primary outcome, with the overall number of potentially inappropriate DDD at 12 months as dependent variable, adjusted for baseline value, taking into account the group allocation.

Generalised linear models will also be used to assess differences in secondary outcomes between the two groups will be tested with the same method as the primary outcome, taking the baseline value and the group allocation as the independent variables, with two-sided $\alpha = 0.05$. If enough supplementary data on falls and hospitalisations are available (see section 7.3 page 19), they will be analysed as the number of falls, respectively the number of hospital days, per mean resident and per year.

All analyses will be made using the Stata statistical package (StataCorp LP, College Station, TX, USA).

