## Statistical analysis

---

The treatment groups were randomly allocated among nursing-homes (NH). The analyst will be blinded with regard to the allocation.

Analyses will be performed at NH level, the NH being the unit of analysis (i.e. there is one data point per NH per variable).

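### The synopsis (62 homes) and section 8.1 (66 homes) disagree on sample size for the same inputs, neither matches the two-sided test on the calculation described, and the randomised physician clusters are not in the analysis

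*Protocol*

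**What the plan says.** The sample size appears in two places in the protocol:

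- Synopsis, number of participants: "62 NHs will be included in this project, 31 in each group (intervention and control"). The entry assumes an SD of 7.5% and a fall from 22.8% to 18.2%. The statistical considerations repeat the claim: "The inclusion of 62 NH will allow for the detection of a 20% relative reduction in the use of PIMs with 80% power".
- Section 8.1, for a mean change of 0 in control and 4.6 in intervention: "common SD of 7.5%, risks of α and β errors of 5% and 20%), 66NH, 33 per group, will have to be included". Sidedness is not given. For ρ = 0.7 the same paragraph says that "the number of NH to include would decrease to 36".

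The planned primary test is in section 8.3. It regresses the change on group and "baseline overall proportion of PIMs as independent variables (two-sided α = 0.05"). The SAP (Inferential analysis) agrees: "NH groups will be compared by means of linear least-square regression under adjustment for baseline". No section of either document plans a one-sided test, and the SAP gives no sample size.

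Section 5.3 groups NHs that share a physician and allocates whole clusters by a 0.5 random draw. It expects mostly pairs, at most one cluster of eight, and some clusters of one. The SAP (Statistical analysis) treats each home as one observation: "the NH being the unit of analysis (i.e. there is one data point per NH per variable". Neither section 8.3 nor the SAP has a term for the physician cluster.

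**The concern.** Two current sections justify the size of the trial with different numbers for identical inputs, so at most one can be right. The figure in 8.1 also does not fit the two-sided test in 8.3, so the claimed 80% power does not follow from the calculation shown. A reader of the final report could not tell which N was planned or for which test.

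The clustering issue is a separate matter and concerns the analysis. The protocol randomises by physician because it expects practice to carry over between homes that share one. If outcomes in those homes are correlated, a regression that treats them as independent understates the standard error, and the nominal 5% test rejects too often. Neither the sample-size calculation nor the model allows for this.

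**Working it through.** **Inputs (section 8.1).** Difference d = 4.6; SD at each time point 6.3; SD of change = 6.3 × √(2(1 − ρ)), which is 7.45 at ρ = 0.3 (stated as 7.5); power 80%; equal arms. The formula is n per group = 2(z_α + z_β)² SD² / d², with z_β = 0.842.

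**1. Reproducing 66.**
- One-sided 5% (z_α = 1.645), SD 7.5: 2 × 6.18 × 56.25 / 21.16 = 32.87, so 33 per group and **66** in total. The t-test version gives 68.
- Two-sided 5% (z_α = 1.960), SD 7.5: 2 × 7.85 × 56.25 / 21.16 = 41.73, so 42 per group and **84** in total. The t-test version gives 86.

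At SD 7.5, 62 is not obtained by any of these four routes.

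**2. Power of the comparison 8.1 describes (unadjusted, SD 7.5; t-test / normal).**

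| NHs | Two-sided | One-sided |
|---|---|---|
| 62 | 66.1% / 67.5% | 77.1% / 77.9% |
| 66 | 68.9% / 70.2% | 79.4% / 80.1% |

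**3. The figure of 36 at ρ = 0.7.** The formula gives SD = 6.3 × √0.6 = 4.88. Two-sided: 17.67, so 18 per group and 36 in total. One-sided: 13.92, so 28 in total. Hence 36 fits the two-sided formula and 66 the one-sided one. The 4.1% printed for ρ = 0.7 does not follow from the protocol's formula; it would need ρ of about 0.79 and would give 26 (two-sided) or 20 (one-sided). The 36 therefore fits 4.9%, and the slip does not affect the chosen N.

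**4. The test actually planned (baseline-adjusted, two-sided, independent NHs, equal arms).** Residual SD = 6.3 × √(1 − ρ²); power from t with N − 3 df.

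| ρ | Residual SD | N for 80% (normal) | Power, 62 | Power, 66 |
|---|---|---|---|---|
| 0.30 | 6.01 | 54 | 84.2% | 86.5% |
| 0.54 | 5.30 | 42 | 91.9% | 93.4% |

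At ρ = 0.3 the difference detectable with 80% power is 4.35 points (62) or 4.21 points (66).

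**5. Physician clusters.** The documents give no intracluster correlation (ICC), so 0.1–0.3 is an assumption. The planned least-squares test was simulated with 62 NHs, ρ = 0.3, each cluster allocated by a 0.5 draw, and the ICC on the residual. The layouts are also assumptions.

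| Layout (62 NHs) | Type I error, ICC 0.1 to 0.3 | Power |
|---|---|---|
| 21 pairs, 20 singletons | about 6% to 7% | 82% to 80% |
| 31 pairs | 6.4% to 8.5% | 81% to 80% |
| One of eight, 19 pairs, 16 singletons | about 6% to 10% | 80% to 79% |
| One of eight, 27 pairs | 6.9% to 10.9% | 80% to 78% |

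A cluster-robust test with small-sample correction (CR2, Satterthwaite df) in the last layout holds type I error at about 5%. Its power is 74% to 64% with 62 NHs and 78% to 68% with 66. At ICC 0, with 62 NHs, power falls from 82% to 77–79%, depending on whether a random effect or CR2 is used.

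**6. Drop-out allowance.** Section 8.3.2 relies on a supplementary recruitment that it places in 8.1, but 8.1 contains none. The second round in section 5.2 is triggered only by insufficient recruitment.

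**The case against.** The strongest defence is that 8.1 is deliberately conservative. It takes ρ = 0.3 although 0.54 was observed, and it ignores the gain from baseline adjustment. Both points stand. A reader might infer from 84 that the trial is 18 to 22 homes short (84 − 66, 84 − 62). The documents do not support that, because 84 belongs to the unadjusted comparison and the adjusted test needs about 54 if homes are independent.

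A reader might also infer that a one-sided calculation was knowingly used. The arithmetic fits, but only under the normal formula, and the origin of the figures is unconfirmed. For example, 62 also matches a two-sided t-test at SD 6.3, and the gap of four could relate to the missing supplementary recruitment. All of this is conjecture. The paragraph appears to mix conventions; that it does so is not established.

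On clustering, the ICC is assumed, and layouts without singletons are less favourable than section 5.3 allows. With pairs and singletons the inflation is mild. It does not vanish, and the SAP's robust variance is offered only for heteroscedasticity.

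The opposite inference, that power is comfortable and nothing further needs saying, also fails, because it assumes independent homes. Nor does the observed year-on-year change settle it. For "the mean difference is 0.8% (IC₉₅ -1.1% - 2.7%, SD 5.3"%), the half-width of 1.9 implies about 32 homes (2.04 × 5.3 / √32 = 1.91), whereas the interval for ρ (0.29–0.72) implies about 44. That SD should not carry a power claim until the two are reconciled.

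**Conclusion.** The point holds as an error in the stated justification. The two values of N conflict for the same inputs. On the calculation 8.1 describes, the two-sided test needs 84 NHs (86 by t-test), and power is 69–70% with 66 and 66–68% with 62, not 80%. These results use only the protocol's own figures.

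The trial is not shown to be underpowered: the planned adjusted model has about 84% (62) or 86% (66) power at ρ = 0.3, provided NHs are independent and arms are equal.

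The missing cluster term is a distinct weakness of the analysis. Its main effect is on type I error, about 6–7% in the mildest layout examined and up to about 11% in the least favourable, for ICCs of 0.1–0.3 that are assumed and not documented. The 4.1% figure and the empty reference in 8.3.2 are minor. Overall this should be fixed before unblinding; confidence is high on the arithmetic, while the size of the cluster effect depends on the unknown ICC and cluster sizes.

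**What to change.** - Give one N in the synopsis and section 8.1, and state two-sided α = 0.05.
- Restate power or the detectable difference for the number enrolled, from the baseline-adjusted model, with residual SD 6.3 × √(1 − ρ²) at ρ = 0.3 and 0.54.
- Add to section 8.3 and the SAP inference that respects the randomised physician clusters, for example small-sample-corrected cluster-robust standard errors or a cluster random effect. Pass a coded cluster identifier to the blinded statistician.
- Report power for that analysis over a stated ICC range with the actual cluster sizes, singletons included. Say plainly that it may fall below 80% (about 64–78% at ρ = 0.3 for 62 or 66 NHs with one cluster of eight and the rest pairs).
- Correct 4.1% to 4.9%, and remove or substantiate the drop-out statement in 8.3.2.
- Record all this as a dated correction before unblinding and list it under section 8.3.4, not as the original a priori justification.

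The cost is a few sentences and one variable that already exists from randomisation. Enrolment, conduct and data collection are unchanged. The downside is that the stated power may look less favourable, the ICC has to be assumed, and the cluster correction costs about 3–5 points of power if homes are in fact uncorrelated.
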